## **OBJECTIVES:**

Principal:

- Evaluate the incidence of CCR and advanced neoplasia in SPS patients with low risk factors of advanced neoplasia during surveillance.

Secondary:

- Compare the incidence of advanced neoplasia between patient surveillance with colonoscopy at 2 and 3 years.
- Describe low risk factors of advanced neoplasia in SPS patient in our environment.
- Identify a group of patients with SPS and low risk of advanced neoplasia.

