Data from all the resected and visualized lesions during the colonoscopy will be collected on the database. A pathologist familiarized with serrated lesions will be in charge of the sample analysis. Serrated lesions will be classified according to WHO criteria for serrated lesions. The investigators define “advanced adenoma” as adenomas  $\geq 10$  mm with villous histology and/or with high grade of dysplasia (HGD). We define “advanced SL” as any SL  $\geq 10$  mm and any SL with dysplasia. The investigators define “advanced neoplasia” as any CRC, any advanced adenoma or advanced SL.

Quality of bowel cleansing will be graded by each endoscopist following the Boston Bowel Preparation Scale. This scale evaluates each segment (ascending colon, transverse colon and descending colon) of the following form: 0 = segment of colon whose mucosa cannot be seen due to the existence of solid stools that cannot be eliminated; 1 = mucosa portion of a colonic segment that can be seen, but other areas of the colonic segment are not seen, either due to the presence of dirt, feces or opaque liquid; 2 = existence of small amount of dirt, small fragments of stool and / or opaque liquid, but the mucosa of the colonic segment can be seen well; 3 = all the mucosa of the colonic segment can be seen well without residual dirt, small traces of stool or opaque liquid. Patients with inadequate preparation (when in any segment the score is 0 or 1, or the total score is less than 6) will be excluded from the study.

During colonoscopy all complications as post-polypectomy bleeding, perforation or cardio-respiratory events will be registered. Those complications will be considered if surgery or hospital admission is required.

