## SAMPLE SIZE CALCULATION

This is a randomized controlled study for evaluating a non inferiority strategy in the surveillance of SPS patients, between colonoscopy in 2 years and colonoscopy in 3 years, with the incidence of advanced neoplasia as the principal aim of the study. In the study from the Netherlands, Bleijenberg and col., the incidence of advanced neoplasia in patients at 2 years surveillance was of 15%. The investigators assume an acceptable increase of advanced neoplasia at 3 years surveillance of 25%, so the margin for no inferiority is 10% between the two groups. Accepting the type I error with an unilateral contrast of 0.025, beta risk of 0.2 (power 80%) and considering a 10% of lost patients, 69 patients in each group (136 in total) are needed to detect significance differences between the two groups.

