## STUDY VARIABLES:

- Demographic variables: Hospital, identification number (number assigned to each hospital and consecutive number of each patient), date of birth, sex, SPS criteria (according to WHO classification and actualized in 2019: 1 or 2), date of the last colonoscopy, number and type of lesions resected at the last colonoscopy, number of previous colonoscopies, number of polyps removed so far (low risk, high risk and serrated lesions), colon surgery (yes/no) and type of surgery (right colectomy, left colectomy, low anterior resection, segmental colectomy or others), smoker (yes/no/prev).
- Variables of the procedure: date of the procedure, bowel preparation according to BBPS scale, study arm (Colonoscopy in 2 years/Colonoscopy in 3 years), number and description of lesions resected during the procedure describing its size, shape according to Paris classification, location of the lesions, distance to the anal margin. Inspection time in each exploration (with stopwatch and without counting the therapeutic moments). Complications during the procedure (bleeding, perforation or cardio-respiratory events).

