## STATISTICAL CONSIDERATIONS AND STATISTICAL ANALYSIS PLAN

Numeric variables will be collected as integer number; they will be presented as mean and standard deviation in case of a normal distribution and compared with a

Student's t test. Categorical variables will be collected associated with an integer starting from cero; they will be presented as frequencies and compared with the Chi Square test. The risk of advanced neoplasia or CRC after 2 year colonoscopy surveillance will be compared with the risk of advanced neoplasia and CRC after 3 year colonoscopy surveillance using logistical regression analysis and expressed as Odds Ratio (OR).

Risk factors identified previously will be assessed in univariate and multivariate Cox Regression analysis, adjusted by age, gender and smoking status). They will be presented as Hazard Ratio (HR) with 95% of confidence interval. Statistical analysis will be performed with SPSS software version 19.0 (SPSS Inc., Chicago, IL, USA).

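### Complications are recorded only during the colonoscopy but counted only if surgery or admission follows, so delayed qualifying events are missed

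*Combined protocol and SAP*

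**What the plan says.** The last paragraph of METHODS sets the recording rule: "During colonoscopy all complications as post-polypectomy bleeding, perforation or cardio-respiratory events will be registered". The next sentence sets the counting rule: "Those complications will be considered if surgery or hospital admission is required". The counting rule carries no time limit.

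STUDY VARIABLES, in the list for the procedure, repeats the recording limit: "Complications during the procedure (bleeding, perforation or cardio-respiratory events". That list shows no onset date, and no admission or surgery resulting from a complication. The colon surgery item elsewhere in the section belongs to the demographic variables and is paired with types of resection, so it does not serve this purpose.

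No section describes a contact after the procedure, a follow-up period for complications or a search of hospital records. Complications appear in no objective; the principal one is "Evaluate the incidence of CCR and advanced neoplasia in SPS patients with low risk factors of advanced neoplasia during surveillance". The statistical section has no analysis specific to complications. Only its general rule for categorical variables could apply: "they will be presented as frequencies and compared with the Chi Square test".

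**The concern.** The recording window and the counting rule do not fit together. The window closes when the examination ends, whereas the counting rule depends on outcomes that may occur or become known later. The first event named, bleeding after polypectomy, can by its name begin once the resection is over.

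What is at stake is the meaning of the complication rate that the trial will report. A reader weighing a 2-year against a 3-year interval would take it as the rate of serious harm per surveillance colonoscopy. If delayed admissions are left out, it is the rate of a narrower class of event and understates that harm. In a multicentre study, some centres might record late admissions on their own initiative and others might not, and the pooled figure would then have no clear definition.

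**Working it through.** The documents contain no complication rate, no timing of complications and no safety sample size, so there is no plan figure to reproduce. The finding rests on setting the two rules side by side.

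**Step 1. What the two rules do to each kind of event**

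| Course of the event | Inside the stated window? | Meets the surgery/admission rule? | Result as written |
|---|---|---|---|
| Begins during the examination, leads to admission or surgery | Yes | Yes | Counted |
| Begins during the examination, controlled there, no admission | Yes | No | Registered, not counted |
| Begins after discharge, leads to admission or surgery | No | Yes | Not recorded |
| Begins after discharge, no admission or surgery | No | No | Not recorded, and would not count anyway |

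The third row is the gap: an event serious enough to count under the plan's own rule is never recorded. The second row is only a severity threshold, which the plan is free to set.

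**Step 2. Direction**

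Let N be the number of examinations, p the true rate of qualifying complications, and f the share that begins after the procedure and goes unrecorded.

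- Expected true count = N × p
- Expected recorded count = N × p × (1 − f)
- Probability that none is recorded = (1 − p(1 − f))^N

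For any f above zero the expected recorded count is below the true one. The proportional shortfall is f itself, whatever N and p are.

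**Step 3. Illustration of size (p and f are assumptions)**

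SAMPLE SIZE CALCULATION gives "69 patients in each group (136 in total) are needed to detect significance differences between the two groups". Twice 69 is 138, not 136; I use the stated total, N = 136. That total already allows for 10% loss, so about 0.9 × 138 = 124 examinations might take place, which would lower every expected count slightly.

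Worked case, p = 2% and f = 50%:

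- True: 136 × 0.02 = 2.72 events
- Recorded: 2.72 × 0.5 = 1.36 events
- Probability of none with full capture: 0.98^136 = 0.064
- Probability of none as recorded: 0.99^136 = 0.255

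Expected recorded events, with the probability of recording none in brackets:

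| Assumed p | f = 0 | f = 25% | f = 50% | f = 75% |
|---|---|---|---|---|
| 0.5% | 0.68 (0.506) | 0.51 (0.600) | 0.34 (0.711) | 0.17 (0.844) |
| 1% | 1.36 (0.255) | 1.02 (0.359) | 0.68 (0.506) | 0.34 (0.711) |
| 2% | 2.72 (0.064) | 2.04 (0.128) | 1.36 (0.255) | 0.68 (0.506) |
| 3% | 4.08 (0.016) | 3.06 (0.045) | 2.04 (0.128) | 1.02 (0.359) |

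The first column shows that the counts are small even with complete capture. Reading across each row shows what the window adds.

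**The case against.** The strongest reply is that the wording is merely loose. Naming bleeding after polypectomy, and counting by surgery or admission, suggests that the authors expected to use later information. That is a possible reading, and it is why confidence is only moderate. It does not rescue the text. The limit appears in two separate sections, no window or method for late events is given in either, and the loose-wording reading calls for the same change.

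A second reply is that the impact is small. This stands. Safety is in no objective, plays no part in the sample size and has no dedicated analysis. The design schedules one surveillance colonoscopy per patient in each arm, so a per-procedure rate does not measure what a longer interval might save through fewer examinations over time.

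A third concerns the variable list. A reader might infer from the missing fields that the admission rule cannot be applied at all. The documents do not support that: the list is a summary and also omits the histology of lesions found at the study colonoscopy, which the endpoint requires. Absence from it does not show that an item will go uncollected.

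Finally, METHODS already registers all complications during the examination, so events controlled on the spot are not lost. Reporting a second rate for them would be a preference, not a correction.

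**Conclusion.** The concern holds in a limited form. Followed as written, the plan omits delayed complications that meet its own counting rule, and the reported rate is too low by the fraction of qualifying events that are delayed. That fraction cannot be derived from the documents. The figures above rest on assumed rates of 0.5% to 3% and assumed delayed shares of 0 to 75%.

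Three stronger conclusions might be inferred and are not supported:

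- **That most qualifying complications arise after the procedure.** The documents give no timing. They support only that such events may arise or become known later.
- **That the recorded rate would be near zero whatever the truth.** In the illustration, true rates of 0.5% to 2% give only 0.68 to 2.72 events with perfect capture, so a low count would owe much to the size of the trial.
- **That the comparison between arms is biased.** The same rule applies to both. If the amount of resection differed between arms, missed late events could differ too, but nothing in the documents shows this.

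The primary endpoint is unaffected. Severity is minor and confidence moderate.

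**What to change.** In the complications paragraph of METHODS and in the procedure variables of STUDY VARIABLES, replace the limit to the procedure with the colonoscopy plus a fixed post-procedure window stated by the sponsor, for example 30 days. State that late events will be sought by the same hospital-record check in both arms and at every centre. Add database fields for date of onset, and for admission or surgery due to the complication. The severity threshold can stay as it is.

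The cost is a short chart check per patient, a few fields and a wording change in two sections. The documents describe no routine contact after the procedure, so the check should not be assumed to fit into an existing visit. The reported complication rate may be less favourable.

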## SAMPLE SIZE CALCULATION

This is a randomized controlled study for evaluating a non inferiority strategy in the surveillance of SPS patients, between colonoscopy in 2 years and colonoscopy in 3 years, with the incidence of advanced neoplasia as the principal aim of the study. In the study from the Netherlands, Bleijenberg and col., the incidence of advanced neoplasia in patients at 2 years surveillance was of 15%. The investigators assume an acceptable increase of advanced neoplasia at 3 years surveillance of 25%, so the margin for no inferiority is 10% between the two groups. Accepting the type I error with an unilateral contrast of 0.025, beta risk of 0.2 (power 80%) and considering a 10% of lost patients, 69 patients in each group (136 in total) are needed to detect significance differences between the two groups.

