CRC prevalence in patients diagnosed with SPS is 15-35%, according to different studies, and the probability at 5 years of developing a CRC is around 1.3-1.9%. During surveillance, the incidence of advanced neoplasia (advanced adenoma or advanced serrated lesions) at 3 years is 13% for adenomas and 42 for serrated lesions. Risk factors for developing CRC and advanced neoplasia have been described in several studies. One of these factors is the SPS criteria 2, which has been demonstrated as a low risk of CRC and advanced neoplasia during surveillance of SPS patients. Detecting more than two sessile serrated lesions proximal to the splenic flexure, one sessile serrated lesion with high grade of dysplasia and the detection of advanced neoplasia in

previous colonoscopies, are all risk factors of developing advanced neoplasia during surveillance. A recent multicentre prospective study established SPS patient surveillance according to lesions detected at last colonoscopy. Individuals with at least one advanced adenoma, an advanced serrated lesion or more than 5 relevant lesions (sessile serrated lesions, adenomas of any size or hyperplastic polyps more than 5 mm) were followed at one year. Patients with no lesions mentioned before were followed at 2 years with colonoscopy. Advanced neoplasia incidence in 2 years recommendation surveillance was 15.6% compared with 24.4% in the 1 year recommendation surveillance. CRC cumulative 5 years incidence was 1.3%. Regarding SPS type, the 5 years advanced neoplasia incidence was lower for patients with SPS criteria III of 2010 (26%) than for patients diagnosed with criteria I (53%) or criteria I and III (59%). In this study patients starting their surveillance with clearing phase achieved (clear colon of all polyps  $\geq$ 5mm and all polyps with the optical aspect of adenoma, TSA or SSL) were at low risk of advanced neoplasia than patients without this phase achieve prior to study inclusion (HR: 0.64; p<0.047).

With all the above described, it can be define a SPS patient with low risk of advanced neoplasia during surveillance: those patients with clearing phase achieved and without any advanced lesion or less than 5 relevant lesions at last colonoscopy.

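### The plan claims 80% power without stating the 3-year incidence it expects, and no reading of its figures gives 80% at 69 per group

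*Combined protocol and SAP*

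**What the plan says.** All the planning inputs are in the sample size section of the combined protocol and SAP. The reference rate comes from an earlier Dutch study: "the incidence of advanced neoplasia in patients at 2 years surveillance was of 15"%. The next sentence is "The investigators assume an acceptable increase of advanced neoplasia at 3 years surveillance of 25"%, followed by "so the margin for no inferiority is 10% between the two groups". The error rates are a beta of 0.2 and "Accepting the type I error with an unilateral contrast of 0.025". Loss is handled by "considering a 10% of lost patients". The result is 69 per group, with a total given as 136.

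The scientific background reports that "Advanced neoplasia incidence in 2 years recommendation surveillance was 15.6"%. From the same study it gives 5-year incidences of 26%, 53% and 59% by SPS criterion. The closing aim of the background is to determine whether incidence is the same at 2 and 3 years. Under Methods, one arm has its colonoscopy at 2 years and the other at 3. The statistical section compares the arms by logistic regression with an odds ratio and does not mention the margin.

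Nowhere is an expected 3-year incidence given for the low-risk patients to be enrolled.

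**The concern.** The power of a non-inferiority test depends on the assumed true difference as much as on the margin. The plan gives a reference rate and a limit, and nothing else. The word used for 25% suggests a tolerance, but the sentence can also be read as the assumed 3-year rate. The two readings lead to very different trials, and neither supports the printed size.

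Equal true rates are the usual default when both arms are observed for the same time. Here the 3-year arm has a further year in which lesions can develop, so some increase is to be expected even if the longer interval is acceptable by the investigators' own limit. If the trial is read as having 80% power, a failure to show non-inferiority could be taken as evidence against 3 years when an inconclusive result was the likeliest outcome from the start.

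**Working it through.** **Inputs.** From the sample size section: 2-year rate 15%, margin 10 points, one-sided 0.025, power 80%, loss 10%. From Methods: 1:1 allocation. From the background: 15.6% at 2 years, 26% at 5 years (2010 criterion III). The multiplier is (1.96 + 0.842)² = 7.849.

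**1. The plan's own figure.** Size per arm is n = [p2(1−p2) + p3(1−p3)] × 7.849 / (0.10 − (p3 − p2))².
- Equal rates of 15%: 0.255 × 7.849 / 0.10² = 200.1, so 201 evaluable. 201/0.9 gives 224 randomised per arm, 448 in total. This is not 69.
- 15% v 25%: the denominator is (0.10 − 0.10)² = 0, so no size exists.
- 15% v 25% with the direction reversed: (0.1275 + 0.1875) × 7.849 / (0.10 + 0.10)² = 61.8, so 62. 62/0.9 = 68.9, so 69. This matches the printed figure.

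The match is an inference. Other inputs also reach 69 (for example equal rates with an 18-point margin: 0.255 × 7.849 / 0.18² = 61.8), but they use values that the plan does not contain. Separately, 2 × 69 = 138, not 136.

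**2. How much the third year might add.** The documents do not give this for the enrolled population. Three calculations, each on a stated assumption:
- Constant rate from 15% at 2 years: p3 = 1 − 0.85^1.5 = 21.6%, or +6.6 points.
- Joining 15.6% at 2 years to 26% at 5 years: (26 − 15.6)/3 = about 3.5 points a year. These are different patient groups.
- Half of the 2-year findings assumed to be lesions missed at baseline, which count in both arms: p3 = 1 − 0.925 × (0.85/0.925)^1.5 = 18.5%, or +3.5 points.

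From a 15% baseline this gives a range of about 18.5% to 21.6%. Projecting back from 26% at 5 years at a constant rate gives 11.3% at 2 years and 16.5% at 3. That 16.5% belongs with 11.3% and cannot be set against 15%.

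**3. Power.** Power = Φ[(0.10 − (p3 − p2)) / √((p2(1−p2) + p3(1−p3))/n) − 1.96], with p2 = 15%. The 62 evaluable come from 69 × 0.9.

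| True 3-year rate | 62 per arm | 201 per arm |
|---|---|---|
| 15% (equal) | 34% | 80% |
| 16% (+1) | 28% | 70% |
| 18.5% (+3.5) | 16% | 42% |
| 21.6% (+6.6) | 7% | 14% |
| 25% (+10) | 2.5% | 2.5% |

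Worked example, 18.5% with n = 201: SE = √((0.1275 + 0.1508)/201) = 0.0372; 0.065/0.0372 − 1.96 = −0.21; Φ(−0.21) = 42%.

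For 80% power the evaluable number per arm would be about 517 at +3.5 points and 2,058 at +6.6 points.

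**The case against.** A reader might infer that the plan assumes the third year adds no risk. The text does not say so. The aim of finding the same incidence points that way, but equal rates would have produced 224 per arm, and the printed 69 is better matched by 25% having been entered for the 3-year arm. The sponsor's assumption is unknown, and that is the point.

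A reader might also infer that the background figures show the third year using up half or more of the margin. They do not. That result needs a constant rate, and about 3.5 points is equally compatible with the same figures. The 5-year incidences are reported by SPS criterion and are not confined to low-risk patients. The enrolled patients have been cleared, which the background associates with lower risk (HR 0.64). Lesions missed at baseline would count in both arms and would not grow with time. The increase could therefore be below 3.5 points.

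These points limit what can be said about the size of the increase. They do not rescue the power claim: one extra point already lowers power to 70% at 201 per arm, and at 62 per arm it is 34% with no increase at all.

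It can also be said that this is only the arithmetic error behind 69. The two are linked, because both turn on which 3-year rate was entered. They are not the same: correcting 69 to 224 under equal rates would still leave a power figure that holds only if the extra year adds nothing.

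**Conclusion.** The concern holds in this form: 80% power is claimed against a 10-point margin with no stated 3-year alternative. At 62 evaluable per arm, power is 34% if the rates are equal, about 16% to 7% if the third year adds 3.5 to 6.6 points, and 2.5% if 25% is the true rate. A correctly sized equal-rates trial of 201 evaluable per arm has about 42% to 14% over the same range.

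The absence of an expected rate and the power at equal rates rest only on the plan's own inputs. The range of +3.5 to +6.6 points rests on the assumptions set out above and is illustrative, not a bound. That 25% was entered with the direction reversed is inferred from the arithmetic. The documents do not support saying that the sponsor assumed no added risk, or that the third year must use up half the margin.

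**What to change.** In the sample size section:
- State the expected 3-year incidence and its basis, separately from the 25% limit, with a range of about 18.5% to 21.6% from a 15% baseline.
- Replace the 80% figure with the power against the existing 10-point margin at that alternative, for the number actually to be enrolled and with the direction of the test correct.
- Reconcile 69 per group with 136 in total.

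In the sample size section and the statistical analysis section:
- Report the risk difference with its confidence interval against the 10-point margin, alongside the odds ratio.
- State that failing to show non-inferiority at this power is not evidence that the 3-year interval is unacceptable.

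The cost is a few sentences in two sections, one further estimate in the analysis, and a much less favourable stated power. No extra patients or procedures are required. The change discloses the power and does not restore it; regaining 80% would need the larger numbers shown in the working.

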## **METHODS**

This is a prospective, randomized (1:1) and multicenter study, in Spanish national hospitals, with SPS patients diagnosed according to the reviewed WHO criteria in 2019, in a surveillance program and who meet all the inclusion criteria and no exclusion criteria.

Inclusion criteria:

- Patients aged 18 years or older that fulfil WHO criteria 1 or 2 of SPS.
  - Criteria 1: any patient with  $\geq 5$  SL proximal to the rectum, all  $\geq 5$  mm in size, with at least 2  $\geq 10$  mm in size.
  - Criteria 2: any patient with  $>20$  SL of any size distributed throughout the colon, with  $\geq 5$  lesions proximal to the rectum.
- Patients with a previous complete colonoscopy with adequate bowel preparation and with all lesions  $>5$  mm been resected ("clearance colonoscopy"), after the diagnostic of SPS.
- Nor advanced adenoma or serrated lesions at prior colonoscopy, and also either more than 5 relevant lesion (adenoma, SSL or PH $>5$ mm) at prior colonoscopy.

Exclusion criteria:

- Patients with no informed consent or who do not agree to participate in the study.
- Patients with total or partial colectomy.
- Patients with other CCR predisposing syndromes with germinal mutation (Familial adenomatous polyposis, Lynch syndrome, Peutz-Jehgers syndrome, Cowden syndrome, Juvenile polyposis syndrome...).

- Patients with chronic inflammatory bowel disease.
- Patients with coagulation disorders.
- Fragmented lesion or submucosal invasive lesion at last colonoscopy.
- Inadequate colon preparation: any segment of the colon with <2 points in Boston Scale (BBPS).

Patients selected for the study will be randomised in two groups for the surveillance: group 1, surveillance with colonoscopy in two years; group 2, surveillance with colonoscopy in three years. Randomization will be done at the database program (RedCAP).

All colonoscopies will be performed with high definition (HD) system and it will be the choice of the endoscopist whether to use chromoendoscopy with indigo carmine or virtual chromoendoscopy. Protocol bowel preparation will be recommended by each centre. Sedation will be prescribed and decided by the endoscopist during the examination.

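### The plan allows for 10% loss but states no analysis set and no handling of randomised patients who never have the assigned colonoscopy, so loss related to risk could bias the 2-year v 3-year comparison in either direction

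*Combined protocol and SAP*

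**What the plan says.** Under Methods the trial is described thus: "This is a prospective, randomized (1:1) and multicenter study". One arm has its surveillance colonoscopy at two years and the other at three.

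The Sample Size Calculation frames the question as non-inferiority and sets the tolerance: "so the margin for no inferiority is 10% between the two groups". It mentions loss once, as an inflation factor: "considering a 10% of lost patients, 69 patients in each group (136 in total) are needed".

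Under Study Variables, follow-up data are collected as attributes of the examination: "Variables of the procedure: date of the procedure, bowel preparation according to BBPS scale", followed by study arm, lesions, inspection time and complications. There is no item for non-attendance, withdrawal, date last seen or reason.

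The Statistical Analysis Plan compares the risk of advanced neoplasia or CRC after the 2-year and 3-year colonoscopies "using logistical regression analysis and expressed as Odds Ratio (OR". It names no analysis set, no treatment of missing outcomes and no sensitivity analysis.

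**The concern.** Advanced neoplasia is defined by lesion size and histology, so a patient who is not examined has no outcome. A logistic model omits such patients unless the plan says otherwise, and this plan is silent. An attenders-only comparison is unbiased if, within each arm, attendance is unrelated to neoplasia risk. The plan gives no reason to expect that and lists no data on why patients were lost.

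The arms also differ by design in exposure to loss: the 3-year arm has half as long again in which patients can withdraw, move or become unfit for colonoscopy. In a non-inferiority trial, a bias towards no difference works in favour of the claim. A bias the other way could reject an acceptable strategy. Either could pass unnoticed if the analysis never looks at the patients without an outcome.

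**Working it through.** **Inputs from the Sample Size Calculation.** 69 per group, 10% loss, 15% risk in the 2-year arm, 25% as the highest acceptable 3-year risk, 10-point margin, one-sided 0.025. Loss by arm and risk among the lost are not in the documents; the values below are assumptions.

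**The plan's own figure.** 69 × 0.90 = 62.1, so about 62 examined and 7 lost per arm. The 69 itself does not reproduce: a standard non-inferiority formula with 15% in both arms gives 201 per arm before loss and 224 after. Also, 2 × 69 is 138, not 136. Those are separate matters; 69 is used here only as the planned size.

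**Step 1: bias when attenders have 15% in both arms.** Let l be the share lost and r the risk among the lost. The risk in all randomised patients of an arm is 0.15 + l(r − 0.15). The attenders-only difference (3-year minus 2-year) is zero, so it misses

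shift = l3(r3 − 0.15) − l2(r2 − 0.15).

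| Loss, 2-yr / 3-yr | Risk among lost, 2-yr / 3-yr | Shift (points) |
|---|---|---|
| 10% / 10% | 15% / 15% | 0 |
| 10% / 10% | 30% / 30% | 0 |
| 8% / 12% | 30% / 30% | 1.8 − 1.2 = 0.6 |
| 5% / 15% | 30% / 30% | 2.25 − 0.75 = 1.5 |
| 10% / 10% | 15% / 30% | 1.5 |
| 10% / 10% | 15% / 45% | 3.0 |
| 10% / 10% | 30% / 15% | −1.5 |
| 10% / 10% | 45% / 15% | −3.0 |

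The 8% / 12% row is loss at 4% a year, averaging the planned 10%. A positive shift means that attenders alone make the 3-year arm look better than it is.

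**Step 2: bias when the truth lies exactly at the margin (15% v 25%).** If the lost have RR times the attenders' risk, the attenders' risk is p / ((1 − l) + l × RR).

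- RR = 2, loss 10% / 10%: 0.25/1.10 − 0.15/1.10 = 22.7% − 13.6% = 9.1 points.
- RR = 2, loss 5% / 15%: 0.25/1.15 − 0.15/1.05 = 21.7% − 14.3% = 7.5 points (unrounded inputs).
- RR = 0.5, loss 10% / 10%: 0.25/0.95 − 0.15/0.95 = 26.3% − 15.8% = 10.5 points.
- RR = 0.5, loss 5% / 15%: 0.25/0.925 − 0.15/0.975 = 27.0% − 15.4% = 11.6 points.
- RR = 1: 10 points, no bias.

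Combining RR = 3 with 5% / 15% loss gives 5.6 points, a bias of 4.4, but both assumptions are strong.

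**Step 3: extreme bound.** If all 7 lost 3-year patients have events and none of the 7 lost 2-year patients does, the difference moves by 7/69 = 10.1 points. The opposite case moves it by −10.1.

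**Step 4: can a plausible number of events change the conclusion?** This illustration uses assumed counts, chosen near the boundary. Upper limits are Wald, two-sided 95%, and imputed events are treated as known.

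- Examined only, 10/62 (2-year) v 8/62 (3-year): difference −3.2, upper limit −3.2 + 12.4 = 9.2. Non-inferior.
- One event among the lost in each arm, 11/69 v 9/69: difference −2.9, upper limit 8.8. Non-inferior.
- One event among the lost 2-year patients and two among the lost 3-year patients, 11/69 v 10/69: difference −1.4, upper limit 10.5. Not shown.

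Newcombe limits for the first and third cases are 9.5 and 10.8, so the result does not depend on the interval method.

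**The case against.** Several points on the other side stand.

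- A reader might infer that the plan has chosen a complete-case analysis. It has not. No sentence names the analysis set, and examined-only is what follows by default from a model that needs a colonoscopy outcome. The defect is silence.
- A reader might set the 10% loss against the 10-point margin and conclude that loss could consume the margin. One is a share of patients and the other a difference in risk. They coincide only when every lost patient in one arm has an event and none in the other does.
- A reader might infer that the bias favours the 3-year arm. The documents do not show this. Greater loss in that arm is possible because of the longer wait, but it is not stated, and if the lost have lower risk the bias reverses.
- A reader might infer that loss could not be checked at all. Randomisation is in the study database, so patients without a procedure can be counted by arm. Baseline items (SPS criterion, lesions at the last colonoscopy, polyp history, smoking) allow attenders and non-attenders to be compared. What is missing is the reason and date of loss and any stated intention to look.
- At the planned size, sampling error dominates. With 62 per arm at 15%, the 95% half-width is 1.96 × √(2 × 0.15 × 0.85 / 62) = 12.6 points, so an observed difference of zero already fails the margin. This limits the practical weight of a shift of one or two points. It does not remove the point, because a larger sample narrows the interval and leaves the bias unchanged.

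**Conclusion.** The point holds as a gap in the plan. Loss is anticipated, exposure to it differs by a year between arms, and nothing says how patients without an outcome enter the comparison. The likely size is modest: roughly 0.6 to 3 points in either direction under most of the assumed scenarios, more only under strong combined assumptions, and zero if the lost have the attenders' risk. The 10.1-point figure is a bound, not a forecast. The split of loss and the risk among the lost are assumptions throughout; the documents give only the overall 10%. They do not support saying that the trial will be biased, or in which direction. They do support saying that a result near the margin could turn on one extra event among the lost, and that the plan contains no analysis that would reveal it.

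**What to change.** **Study Variables.** For every randomised patient without the assigned examination, record the date last seen and, where the hospital record holds it, the reason.

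**Statistical Analysis Plan.**

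1. Define the primary set as all randomised patients in their assigned arm, and state how missing outcomes are handled in the base case, for example by imputation within arm from the baseline variables already collected.
2. Report the number lost, and the baseline risk of attenders and non-attenders, by arm.
3. Give the 2-year v 3-year comparison as a risk difference with its confidence interval, set against the 10-point margin. The plan now reports only an odds ratio, and the next step cannot be run without this.
4. Add a tipping-point analysis that varies risk among the lost in both arms and in both directions, and report where the conclusion changes. State in advance what excess risk would count as plausible, and qualify any non-inferiority claim that reverses within it.

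**Cost.** Two extra fields and one extra analysis, with no additional procedures. The reason will be incomplete for some patients, particularly those who move away, and is best recorded as losses occur. The real downside is that a favourable result may have to be reported as less certain.
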